7.2. Clinical Laboratory Data

All laboratory parameters collected at each center's local laboratory will be normalized by converting values in original units to values in SI units and classified as normal, low, or high based on normal ranges supplied by the local laboratories and upon employing standardization.

Observed and change from baseline clinical laboratory data (hematology, chemistry and urinalysis) will be summarized by treatment group and protocol specified time points for the following clinical laboratory variables.

Hematology	Hemoglobin, hematocrit, red blood cells (RBC), platelet count, white blood cell count (WBC)– total and differential.
Biochemistry	Aspartate transaminase, alanine transaminase, alkaline phosphatase, sodium, potassium, chloride, bicarbonate, blood urea nitrogen (BUN), bilirubin (total, direct and indirect), creatinine, creatine kinase, glucose, and albumin.
Urinalysis	Glucose, specific gravity, blood, ketones, protein, bilirubin, pH, urobilinogen, leukocyte esterase, and nitrite.

Clinical laboratory test values are potentially clinically significant (PCS) if they meet either the low or high PCS criteria listed in [Table 3](#). The number and percentage of subjects with baseline and/or post-baseline PCS values will be tabulated by treatment group and overall.

The percentages will be calculated relative to the number of subjects with available values for

each lab parameter in each treatment group at the analysis visit. The numerator is the total number of subjects with at least 1 PCS value at the analysis visit. A supportive listing of subjects with post-baseline PCS values will be provided including the subject number, site, baseline, and post-baseline values.

Table 3: Criteria for Potentially Clinically Significant Laboratory Tests

Parameter	SI Unit	Lower Limit	Higher Limit
Biochemistry			
Albumin	g/L	<25 g/L	
Alanine Aminotransferase (ALT)	U/L		≥3*ULN
Alkaline Phosphatase (ALP)	U/L		≥3*ULN
Aspartate Aminotransferase (AST)	U/L		≥3*ULN
Bilirubin, Direct	umol/L		>1.5*ULN
Bilirubin, Total	umol/L		>1.5*ULN
Bicarbonate	mmol/L	<LLN	
Blood Urea nitrogen	mmol/L		>2.5*ULN
Chloride	mmol/L	<90 mmol/L	>115mmol/L
Creatinine	umol/L		≥178.8 umol/L
Creatine kinases	U/L		≥3*ULN
Glucose	mmol/L	<3.05 mmol/L	≥8.88 mmol/L
Potassium	mmol/L	<3.5 mmol/L	>5.5 mmol/L
Sodium	mmol/L	<130 mmol/L	>150 mmol/L
Hematology			
Hemoglobin	g/L	<0.9*LLN	
Hematocrit	%	<0.9*LLN	
Platelet Count	10 ⁹ /L	<LLN	
Urinalysis			
Specific Gravity		<0.9*LLN	>1.1*ULN
pH		<LLN	
Protein			>2+
Glucose			>1+
Blood			>2+

LLN: Lower limit of normal value provided by the laboratory
 ULN: Upper limit of normal value provided by the laboratory

Descriptive statistics will be used for continuous data and frequency counts and percentages for categorical data. A shift table from baseline, by treatment group and protocol specified time points, of normal, abnormal low, and abnormal high records will also be summarized for hematology and chemistry data with marginal totals using frequency counts and percentages.

All laboratory data will be listed for the safety set.

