2.2.5. Safety Endpoints

- Incidence and severity of ocular and systemic treatment-emergent adverse events.
- Incidence of ADA directed against pegcetacoplan peptide or PEG.
- Incidence of new active CNV in the study eye.
- Incidence of new onset of subclinical CNV in the study eye.
- Incidence of subjects who lost letters based on NL-BCVA categories (≥ 15 , $\geq 15 - < 30$, ≥ 30 ETDRS letters).
- Change/shift from baseline in clinical labs and incidence of abnormal lab values.
- Change from baseline in vital signs and incidence of abnormal vital sign results.
- Shift from baseline in ocular examination assessments including slit-lamp examination and indirect ophthalmoscopy.
- Change from baseline in Intra Ocular Pressure (IOP) and incidence of IOP above specified thresholds.
- Change/shift from baseline in ocular imaging assessments (including specular microscopy; select sites).

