7.3. Vital Signs

Descriptive statistics for vital signs (e.g., systolic and diastolic blood pressure, respiratory rate, temperature and pulse rate) and their changes from baseline at each post-baseline visit will be presented by treatment group and overall.

Vital sign values will be considered PCS if they meet both the observed value criteria and the change from baseline criteria listed in Table 4. The number and percentage of subjects with PCS baseline and/or post-baseline values will be tabulated by treatment group and overall. The percentages will be calculated relative to the number of subjects with values for each vital sign parameter in each treatment group at the analysis visit. The numerator is the total number of subjects with at least 1 PCS vital sign value at the analysis visit. A supportive listing of subjects with post-baseline PCS values will be provided including the subject number, site, baseline, and post-baseline PCS values.

Table 4: Criteria for Potentially Clinically Significant Vital Signs

Vital Sign Parameter	Flag	Criteria ^a	
		Observed Value	Change from Baseline
Systolic blood pressure (mmHg)	High	≥180	Increase of ≥20
	Low	≤90	Decrease of ≥20
Diastolic blood pressure (mmHg)	High	≥105	Increase of ≥15
	Low	≤50	Decrease of ≥15
Pulse rate (beats per minute)	High	≥120	Increase of ≥15
	Low	≤50	Decrease of ≥15

^a A post-baseline value is considered as a PCS value if its meets both criteria for observed value and change from baseline.

All vital signs data will be listed for the safety set.

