7.5. Complete Ophthalmic Exam

Results of the ocular assessments will be summarized by shift tables showing the shift from baseline in the individual slit-lamp examination and indirect ophthalmoscopy endpoint. These will be provided by treatment group, overall and visit for study eye and fellow eye. The visits to be presented are Month 12, Month 24, and LOV.

Any relevant findings from the post-baseline ophthalmic examination are to be reported as AEs.

The change from baseline in chronic (first measurement of the day) IOP will be summarized over time by treatment group. In addition, the incidence of IOP above specified thresholds (i.e., >21 mmHg at pre-injection/chronic (first measurement of the day); >30 mmHg post injection) will be summarized by treatment group and overall, protocol specified timepoint (at Month 12 and Month 24 readout, respectively) and over the whole study.

The mean change from baseline in the chronic IOP \pm the standard error will be plotted over time by treatment group.

Details of the ocular assessments will be provided in listings for the safety set and for IOP, the ITT set.

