13.6. Repeated or Unscheduled Assessments of Safety Parameters

If a subject has repeated assessments before the start of investigational product, then the results from the final assessment made prior to the start of investigational product will be used as baseline. If end-of-study assessments are repeated or unscheduled, the last post-baseline assessment will be used as the end of study assessment for generating descriptive statistics. However, all post-baseline assessments will be used for PCS value determination and all assessments will be presented in the data listings.

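### The laboratory PCS table and the chronic IOP >21 mmHg table set no condition on baseline status, so they report prevalence where SAP 2.2.5 names incidence

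*SAP*

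**What the plan says.** SAP 2.2.5 lists two safety endpoints that matter here: "Change/shift from baseline in clinical labs and incidence of abnormal lab values" and "Change from baseline in Intra Ocular Pressure (IOP) and incidence of IOP above specified thresholds".

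For laboratory values, SAP 7.2 defines potentially clinically significant (PCS) by the absolute limits in Table 3 alone. The table is described as "The number and percentage of subjects with baseline and/or post-baseline PCS values will be tabulated by treatment group and overall". The denominator is set by "The percentages will be calculated relative to the number of subjects with available values for" each parameter in each group at the visit, and "The numerator is the total number of subjects with at least 1 PCS value at the analysis visit". SAP 13.6 adds that "all post-baseline assessments will be used for PCS value determination".

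For pressure, SAP 7.5 plans "the incidence of IOP above specified thresholds (i.e., >21 mmHg at pre-injection/chronic (first measurement of the day"), together with >30 mmHg after injection. Both are given by timepoint and over the whole study. Nothing is said about pressure at baseline.

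Elsewhere the SAP does take baseline into account. For vital signs, "Vital sign values will be considered PCS if they meet both the observed value criteria and the change from baseline criteria". The exudative AMD incidence in SAP 7.1.1 leaves out subjects with a history of CNV in that eye. A treatment-emergent antibody response in SAP 7.8 requires a negative baseline result.

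**The concern.** Incidence means new occurrence among those still free of the event. A count of everyone beyond a limit at a visit, over everyone measured there, is prevalence. Safety labs are scheduled at five post-baseline visits (Months 2, 6, 12, 18 and 24). A subject who was PCS before dosing and stays so can appear in all five rows, in any arm. An eye that starts above 21 mmHg needs only one later first-of-day reading above 21 to enter the whole-study IOP count.

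Such baseline excess is possible. Subjects are at least 60 years old. Exclusion 15 removes only laboratory values that the investigator judges clinically significant and unsuitable. Exclusion 4 names only uncontrolled glaucoma or ocular hypertension. Some Table 3 limits are not extreme, such as glucose of 8.88 mmol/L or more, or platelets below the lower limit of normal. With balanced arms, the same background is added to each arm, and this makes a real harm look smaller.

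**Working it through.** **Plan's own figure.** There is none to reproduce. The documents give no baseline rate of PCS values or of IOP >21 mmHg, and no precision for safety tables. The only input taken from them is 200 subjects per analysis group (SAP 3.4, with sham pooled). The rest are assumptions, shown over a range.

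**Model.** Let b be the share beyond the limit at baseline and q the share of these counted again after baseline, both equal across arms. Let i0 and i1 be the new-onset risks on sham and drug among the rest.

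- Reported rate in an arm: b·q + (1−b)·i
- Risk difference as tabulated: (1−b)·(i1−i0)
- Risk ratio as tabulated: [b·q + (1−b)·i1] / [b·q + (1−b)·i0]

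**One case in full.** Take i0 = 2%, i1 = 6%, b = 5%, q = 1. Sham is 0.05 + 0.95×0.02 = 6.90%. Drug is 0.05 + 0.95×0.06 = 10.70%. The difference is 3.80 points and the ratio 10.70/6.90 = 1.55. Restricted to the 200×0.95 = 190 subjects per group within the limit at baseline, the difference is 4.00 points and the ratio 3.00.

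**Range, with i0 = 2% and i1 = 6%:**

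| b | q | Sham | Drug | Difference (points) | Ratio |
|---|---|---|---|---|---|
| 0 | – | 2.00% | 6.00% | 4.00 | 3.00 |
| 0.5% | 1 | 2.49% | 6.47% | 3.98 | 2.60 |
| 2% | 1 | 3.96% | 7.88% | 3.92 | 1.99 |
| 5% | 1 | 6.90% | 10.70% | 3.80 | 1.55 |
| 5% | 0.5 | 4.40% | 8.20% | 3.80 | 1.86 |
| 10% | 1 | 11.80% | 15.40% | 3.60 | 1.31 |
| 20% | 1 | 21.60% | 24.80% | 3.20 | 1.15 |
| 20% | 0.5 | 11.60% | 14.80% | 3.20 | 1.28 |

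**Second set, with i0 = 5%, i1 = 10%, q = 0.9 (true ratio 2.00).** At b = 5% the rates are 9.25% and 14.00%, so the ratio is 1.51 and the difference 4.75 points. At b = 20% they are 22% and 26%, so the ratio is 1.18 and the difference 4.00 points. The binomial standard error of the difference, √[p0(1−p0)/n + p1(1−p1)/n], is 3.2 points with all 200 per group at b = 5%, against 2.7 with the 190 at risk. At b = 20% it is 4.3 points with 200, against 2.9 with 160.

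The ratio and the precision are sensitive to b. The risk difference loses only the share b of its size.

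**What the other planned outputs show.**

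- SAP 7.2 plans a shift table from baseline (normal, low, high) by arm and timepoint, for hematology and chemistry. Where the PCS limit equals the normal limit (platelets, bicarbonate), this already shows new onset by visit. Where the limits differ (ALT at 3×ULN, hemoglobin at 0.9×LLN), a subject who goes from mildly abnormal to PCS stays in the same cell.
- Urinalysis is not in the shift table.
- The PCS listing gives each subject's baseline value, but no rate by arm.
- In SAP 7.5 the shift tables cover slit-lamp and indirect ophthalmoscopy. IOP gets change from baseline, summarized and plotted, which does not count threshold crossings.

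**The case against.** The case against a change is that these are descriptive tables without hypothesis tests, and that new onset is already shown elsewhere. Besides the shift table and listing, protocol 9.6 has clinically significant laboratory values recorded as adverse events, SAP 7.5 does the same for relevant ophthalmic findings, and a TEAE must start or worsen after the first dose. Several Table 3 limits are extreme, and exclusion 15 applies, so b may be close to zero for them. In the study eye, exclusion 4 and the condition in protocol 7.3.4 that pressure be 21 mmHg or below before injection probably keep b low.

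Most of this stands and limits the point. It does not remove it. Adverse event recording rests on the investigator's judgment and not on the PCS limits. Protocol 7.3.4 allows medication to lower the pressure before dosing, while the table uses the first reading of the day. The fellow eye is not bound by either IOP rule.

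A reader might infer more than the text supports:

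- That a subject who is PCS only at baseline inflates the post-baseline rows. The numerator is per analysis visit, and SAP 13.6 speaks of post-baseline assessments, so only persistent or recurrent cases do. The and/or wording is ambiguous and most naturally means a baseline row beside later ones.
- That a chance baseline imbalance would pass unnoticed as a drug effect. Such a baseline row would show it for labs, and SAP 5.2 summarizes baseline IOP by arm.
- That no subject-level count is planned. SAP 7.5 includes one over the whole study for IOP. For labs, 7.2 read with 13.6 is unclear.
- That protocol 7.3.4 predicts readings above 21 mmHg. It only sets a condition for dosing.

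**Conclusion.** The point holds in a limited form. Neither table conditions on baseline, so each gives the share of subjects beyond a limit at a visit or over a period, under an endpoint called incidence. No planned output gives new onset by arm at PCS limits that differ from the normal range, for urinalysis, or for IOP >21 mmHg. The >30 mmHg post-injection count is unaffected, as are the efficacy tests.

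With balanced arms and equal persistence, any dilution runs toward no difference. Its size rests entirely on b, q and the onset rates, none of which the documents give. It is nil at b = 0, small where baseline excess is rare, and mainly a matter of the ratio and the noise. The change is worth making because it costs little and these tables are where a reader will look for a pressure or laboratory signal.

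**What to change.** Keep the all-subject rows, label them as prevalence, and state that a baseline row is shown. Add treatment-emergent rows by arm.

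- **SAP 7.2.** Numerator: subjects with at least one post-baseline PCS value, using all post-baseline assessments as SAP 13.6 says. Denominator: subjects with a baseline value that is not PCS in that direction and at least one post-baseline value.
- **SAP 7.5.** Numerator: eyes with a post-baseline first-of-day reading above 21 mmHg. Denominator: eyes whose baseline first-of-day reading is 21 mmHg or below and that have a post-baseline reading. Report study and fellow eye separately, and show eyes above 21 at baseline in their own row. Use the first reading of the day for baseline here, because the general rule in SAP 13.2 takes the last pre-treatment value, which may follow pressure-lowering medication.

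The cost is SAP wording and one filter per table, with no new data. The added rows have smaller denominators (190 of 200 per group at b = 5%, 160 at 20%). Threshold counts also do not show worsening in those already beyond the limit, so the change-from-baseline summaries and the shift table should stay.

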13.7.6. Character Values of Clinical Laboratory Variables

If the reported value of a clinical laboratory variable cannot be used in a statistical analysis (e.g., a character string is reported for a numerical variable), the appropriately determined coded value will be used in the statistical analysis, several examples are shown in [Table 7](#) for an illustration purpose. The actual values as reported in the database will be presented in data listings.

Table 7: Examples for Coding of Special Character Values for Clinical Laboratory Variables

Clinical Laboratory Test	Possible Results (in SI units)	Coded Value for Analysis
Chemistry: Bilirubin, Total/Direct	<1.7	0.85
	<2	1
Urinalysis: Specific Gravity	≤1.005	0.5025
	>1.030	1.030
Urinalysis: Glucose	≥55	Positive
	≤0	Negative
Urinalysis: pH	≥8.0	8.0
Urinalysis: Protein	≥500	500
Other: FSH	<0.2	0.1

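### No genuine result can meet the SAP Table 3 specific-gravity limits; as written, the row can contain only artefacts of the Table 7 coding

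*SAP*

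**What the plan says.** SAP Section 7.2 defines the flag: "Clinical laboratory test values are potentially clinically significant (PCS) if they meet either the low or high PCS criteria" in Table 3. Meeting either limit is enough. In the urinalysis block, the row "Specific Gravity" has a low limit of 0.9 times LLN and a high limit of 1.1 times ULN. The table footnotes define these as "LLN: Lower limit of normal value provided by the laboratory" and "ULN: Upper limit of normal value provided by the laboratory". Neither the SAP nor the protocol gives a number for them.

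Two other sections decide which values meet these limits.

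- SAP Section 13.7.6 deals with results reported as character strings: "the appropriately determined coded value will be used in the statistical analysis". In its Table 7, the row "Urinalysis: Specific Gravity" codes a result of ≤1.005 as 0.5025 and a result of >1.030 as 1.030.
- SAP Section 13.6 states that "all post-baseline assessments will be used for PCS value determination", so one flagged record at any time after baseline is enough to count a subject.

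Section 7.2 plans the number and percentage of subjects with PCS values by treatment group, with a supporting listing. Its normal/low/high shift table covers hematology and chemistry only. Incidence of abnormal laboratory values is a safety endpoint in SAP Section 2.2.5.

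**The concern.** Table 3 applies the same 0.9 × LLN limit to hemoglobin and hematocrit, where a 10% shortfall is a meaningful departure. Specific gravity is a ratio to water, and all its information lies in the second and third decimals above 1. Ten per cent of such a number is several times wider than the whole span of results that the SAP shows. A limit set that way cannot separate an abnormal result from a normal one.

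At stake is whether the PCS row means anything. Because the shift table leaves out urinalysis, this row is the only categorical tabulation of abnormal specific gravity specified in Section 7.2. An empty high side could be taken as evidence that no concentrated urine was seen. A populated low side could be taken as a finding when it comes only from how a character result was coded.

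**Working it through.** **Inputs.** Limits of 0.9 × LLN and 1.1 × ULN (SAP Table 3). Codes of 0.5025 for ≤1.005 and 1.030 for >1.030 (SAP Table 7). Reference limits are assumed, because the documents give none: LLN 1.000 to 1.010, ULN 1.020 to 1.040.

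**Step 1: reproduce the plan's own code.** The Table 7 rows with an upper bound and a numeric code follow a half-of-the-limit rule:

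- bilirubin: 1.7 / 2 = 0.85 and 2 / 2 = 1
- FSH: 0.2 / 2 = 0.1
- specific gravity: 1.005 / 2 = 0.5025

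All four match the table. Halving a limit near zero does little harm. Halving one near 1 gives a value that no urine sample can have.

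**Step 2: low limit, 0.9 × LLN.**

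| Assumed LLN | 0.9 × LLN | 1.000 flagged? | 1.005 flagged? | Coded 0.5025 flagged? |
|---|---|---|---|---|
| 1.000 | 0.9000 | no | no | yes |
| 1.005 | 0.9045 | no | no | yes |
| 1.010 | 0.9090 | no | no | yes |

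Break-even values: a reading of 1.000 is flagged only if LLN exceeds 1.000 / 0.9 = 1.111. The coded 0.5025 is flagged whenever LLN exceeds 0.5025 / 0.9 = 0.558.

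**Step 3: high limit, 1.1 × ULN.**

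| Assumed ULN | 1.1 × ULN | 1.030 flagged? | 1.050 flagged? |
|---|---|---|---|
| 1.020 | 1.122 | no | no |
| 1.030 | 1.133 | no | no |
| 1.040 | 1.144 | no | no |

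Break-even value: 1.030, the code for >1.030, is flagged only if ULN is below 1.030 / 1.1 = 0.936.

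**Step 4: scale of the mismatch.** At ULN 1.030 the margin is 0.1 × 1.030 = 0.103. The span between the two Table 7 bounds is 1.030 − 1.005 = 0.025. The margin is therefore 0.103 / 0.025 = about 4 times that span.

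**Step 5: combine the tables.**

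- *As written:* the high count is zero. The low count is the number of subjects with at least one result reported as ≤1.005, all of them flagged by the code and not by the reading.
- *Table 7 low code corrected, Table 3 unchanged:* 1.005 is above 0.9 × LLN throughout the range, so the low count also becomes zero and the whole row is empty.
- *Table 3 changed to <LLN and >ULN, Table 7 unchanged:* 0.5025 is still below any LLN in the range, so the false low flags remain. A >1.030 result, coded 1.030, does not exceed ULN when ULN is 1.030 or higher, so it is missed.

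Neither table can be repaired without the other.

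**The case against.** A reader who looks only at Table 3 might infer that the row must show 0% in every arm. The documents do not support that. Section 13.7.6 puts the coded value into the analysis, and 0.5025 lies below 0.9 × LLN for any plausible LLN. On the low side the written plan therefore produces false positives, not false reassurance. An empty row follows only on the high side, or on both sides if the Table 7 low code is corrected alone.

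The other objections concern evidence and weight.

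- *The reference limits are not in the documents.* True, but the break-even values of 1.111 and 0.936 are so far from any usable range that the conclusion does not depend on the exact limits.
- *Table 7 is offered only as examples.* True, but specific gravity is one of the examples, with both codes spelled out.
- *Nothing is lost from safety review.* Largely right. Section 7.2 also summarises observed values and changes from baseline, classifies all laboratory parameters as normal, low or high, and lists all the data. Protocol Section 9.6 requires clinically significant laboratory values to be recorded as adverse events. One reservation: if 0.5025 also enters the means and changes, each such record is displaced by 1.005 − 0.5025 = 0.5025, about 20 times the 0.025 span, so those summaries are not a clean fallback.
- *Unscaled limits only repeat the low/high classification and do not define clinical significance.* This stands in part, and it is why dropping the row is a reasonable alternative.

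**Conclusion.** The point holds in this form: the Table 3 limits for specific gravity cannot be met by any genuine result. They lie at about 0.90 to 0.91 and 1.12 to 1.14. As the SAP stands, the high side is always empty and the low side can contain only coding artefacts, so the row carries no information about real extremes.

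This rests on the assumed reference ranges (LLN 1.000 to 1.010, ULN 1.020 to 1.040), on genuine readings lying at or above 1.000 and not approaching 1.12, and on Table 7 being applied as printed. The number of false low flags cannot be estimated, because the documents do not say how often ≤1.005 is reported.

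Severity is low. One urinalysis row in a safety table is affected, and no hypothesis test or efficacy estimate. It is worth correcting because it is plainly wrong and cheap to repair.

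**What to change.** In SAP Table 3, replace the specific-gravity limits with unscaled <LLN and >ULN. The table already uses an unscaled <LLN for urine pH, bicarbonate and platelets. Alternatively, drop the row if specific gravity is not of interest as a PCS parameter.

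If the row is kept, amend Table 7 at the same time:

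- Code ≤1.005 at its limit, 1.005, and do not halve it.
- Code >1.030 just above 1.030, or classify it directly against the laboratory's normal range.

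Direct classification is safer where a laboratory's ULN is above 1.030, because a result known only to exceed 1.030 may or may not exceed that ULN.

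The cost is one row in Table 3 and two codes in Table 7. The small downside is more flags, some of no clinical interest.
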